2.0 Background/Scientific Rationale

While there is concern for over-treatment of prostate cancer (PCa) it remains the 2nd leading cause of cancer death in U.S. men (1). This paradox is due in part to the accuracy limitations of current detection methods of serum prostate specific antigen (PSA) and digital rectal examination (DRE) screening, and the inability of current clinical information to discriminate indolent from aggressive tumors. Clinical patient characteristics including age, race, family history of PCa, DRE, and prior negative prostate biopsy history have been combined into a predictive calculator to guide biopsy decisions(2). Men found to have adequate suspicion for PCa require a tissue diagnosis. Standard PCa detection relies on 12-core transrectal ultrasound (TRUS) guided biopsy that samples anatomic zones of the prostate gland. Approximately 35% of men undergoing immediate radical prostatectomy (RP) for low grade PCa on standard biopsy will be found to have higher grade tumors in the pathologic specimen(3). Furthermore, between 30-38% of men with clinical suspicion for PCa and a negative standard biopsy will be diagnosed with PCa on re-biopsy(4). Finally, TRUS biopsy is an invasive procedure with a rate of sepsis as high as 2%, and this risk is proportional to the number of biopsy cores sampled(5). With a more precise method for early detection of the most aggressive tumors, men with indolent PCa could be spared treatment with its associated cost and morbidities and instead be managed conservatively with active surveillance (AS), while those with potentially lethal disease could be expediently referred for radiation or surgery with curative intent.

Improved PCa detection may be particularly important for African American (AA) men, who are almost twice as likely to die from PCa as white men(1). A recent study of men with very low risk PCa based on clinical information who underwent immediate RP found that AA men were more likely to have adverse RP pathology and anteriorly located tumors not reached with standard TRUS prostate biopsies(6). In addition, two series of men selected for AS based on standard clinical information reported that AA men progressed to treatment faster than white men(7, 8). These data have questioned the safety of managing AA men with AS without more accurate risk stratification tools such as imaging. At UIC, over 60% of PCa cases diagnosed are in AA men.

[figure not shown]

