When compared to RP histology, ADC has a moderate inverse correlation with PCa grade (ref ADC and grade). With conventional DWI the calculation of ADC assumes a gaussian distribution of water molecule diffusion and tissue homogeneity which may oversimplify water motion in organs with complex tissue structures. A technique that more accurately determines water diffusion through tissues may better discriminate cancer grade. As such, we have tested stretched exponential (SEM) and kurtosis models of DWI with high b-values to determine the grade of PCa in 31 men undergoing biopsy targeted to MRI lesions identified using standard PI-RADS scoring. We found accuracy as measured by area under the receiver operator curve (AUC) that is significantly improved over PI-RADS, the PBCG model, and modestly improved over conventional ADC (Figure 2). Therefore, we propose to prospectively use quantitative DWI as a biomarker to determine regions of the prostate suspicious for high grade PCa in biopsy naïve men.

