3.0 Objectives/Aims

This study aims to determine whether a detection specific MRI protocol with quantitative image analysis can improve high grade PCa detection in men with clinical suspicion and no prior biopsy.

Aim 1: Design a PCa detection specific MRI protocol which will facilitate quantitative image analysis and reduce study time by ~50%

Current prostate mpMRI protocols include image sequences and fields of view outside of the prostate gland and its immediate surrounding that are not useful for PCa detection. We will create a detection specific MRI protocol featuring: smaller fields of view zoomed to the prostate, T2 weighted imaging at multiple echo times, chemical exchange saturation transfer imaging (CEST), and DWI at higher b values (up to 4000) that will allow for quantitative prediction of high grade PCa. The exact imaging acquisition parameters can be found in Appendix 3. We expect this MRI protocol to

reduce study (acquisition) time from approximately 45 minutes to 27 minutes, which will potentially lower cost and improve tolerance of the procedure. Significantly, we will omit DCE which will reduce the imaging time, and the risks associated with intravenous contrast including systemic fibrosis, and patient discomfort.

Aim 2: Determine the accuracy of the novel MRI protocol for detection of high grade PCa

50 men with clinical suspicion of PCa (elevated PSA and/or abnormal DRE) will be enrolled into a prospective protocol and will undergo detection protocol MRI described in Aim 1. Quantitative image analyses will be performed to generate SEM maps of DWI. Areas of suspicion for high grade PCa (GS ≥ 7) will be targeted for biopsy. Men with MRI with no areas of suspicion for high grade PCa will undergo standard of care 12 core TRUS biopsy. The primary endpoint will be the rate of detection of high grade PCa on the per patient and per biopsy core basis. Men with biopsy pathology negative for PCa will undergo standard of care (SOC) continued monitoring.

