12.0 Statistical Considerations

As this is a single arm pilot study, no power analysis is necessary. Based on the PRECISION study, we expect a high grade PCa detection rate of approximately 30% or in 17/50 subjects (10). The primary outcome will be the comparison of the rate of high grade PCa detection based on the 2 possible MRI outcomes: men undergoing standard

12 core TRUS biopsy (detection protocol MRI negative) versus men undergoing MRI targeted biopsy (detection protocol MRI positive for lesions). This will be analysed for statistical difference using the chi-square test. Each MRI quantitative parameter will be evaluated on a per lesion basis as a predictor of high grade PCa using ROC logistic regression and will be reported as AUC with 95% confidence intervals (CI). The Youden's Index and 90% fixed sensitivity thresholds of each quantitative parameter will be reported. Combinations of MRI quantitative and clinical parameters will be combined into multinomial logistic regression models for which AUC with 95% CI will be reported. The AUC of the multi-parametric models will be compared iteratively for statistical differences using the likelihood ratio test.

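### Section 12 estimates clinical effects from about 15 to 17 high grade cases instead of using the PBCG score from the preliminary work, so the combined AUC will be reported too high

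*Combined protocol and SAP*

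**What the plan says.** Section 2.0 describes a published calculator (reference 2) that draws on age, race, family history, DRE and earlier negative biopsy. It then reports the team's preliminary work on diffusion models "to determine the grade of PCa in 31 men undergoing biopsy targeted to MRI lesions identified using standard PI-RADS scoring", and concludes: "We found accuracy as measured by area under the receiver operator curve (AUC) that is significantly improved over PI-RADS, the PBCG model". A modest gain over conventional ADC is reported as well.

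Of those three comparators, PI-RADS and ADC reappear among the secondary analyses in the Study Design and Procedures section. PBCG does not. It is absent from the objectives, the outcomes, the data fields in section 8.0 and the methods in section 12.0.

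Section 12.0 says: "Combinations of MRI quantitative and clinical parameters will be combined into multinomial logistic regression models for which AUC with 95% CI will be reported". It lists no clinical predictors, clinical-only reference model, external score or internal validation. Models are to be compared by likelihood ratio test. Single MRI parameters are analysed per lesion; the unit for the combined models is not given. On expected events it says: "we expect a high grade PCa detection rate of approximately 30% or in 17/50 subjects".

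**The concern.** A published score has weights estimated elsewhere, so its AUC in these 50 men owes nothing to fitting. A clinical model whose coefficients are estimated in the same 50 men will separate them better than it would separate anyone else. The plan has the first option available, since the team has already used such a score, but describes only the second.

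Two things are at stake. The preliminary claim against PBCG, made in 31 men selected for having an MRI lesion, would not be tested prospectively. And the combined AUCs, a result that a later study might be designed around, would be too high by an amount the planned confidence interval does not show.

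**Working it through.** **Events.** 50 × 0.30 = 15. The protocol prints 17, which is 17/50 = 34%. Both are carried below, and the two figures should be reconciled.

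**Clinical coefficients.** Section 12.0 names none, so they are counted from the fields in section 8.0. Age 1, race in four categories 3, family history 1 and PSA 1 make 6. Adding IPSS, SHIM and prostate volume makes 9.

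**Events per clinical coefficient, before any MRI term.**
- 6 coefficients: 15/6 = 2.5 and 17/6 = 2.8.
- 9 coefficients: 15/9 = 1.7 and 17/9 = 1.9.

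If only men with a lesion contribute, and the 28% MRI-negative share that section 2.0 quotes from the European randomised trial applied here (an assumption), then 50 × 0.72 = 36 men remain. At the same event rate that is 36 × 0.30 = 10.8 to 36 × 0.34 = 12.2 men with events.

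**Effect on the AUC.** The simulations used 50 men, 30% high grade, 7 clinical coefficients (age, three race indicators, family history, PSA, DRE) and one MRI parameter with log odds ratio 1.0 per SD, 1,500 trials per run. The effect sizes are assumptions. Two separately programmed runs gave:

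| AUC | Run A: trial / new men | Run B: trial / new men |
|---|---|---|
| Clinical, refitted | 0.77 / 0.58 (true 0.66) | 0.76 / 0.56 (true 0.64) |
| Clinical + MRI, refitted | 0.86 / 0.69 (true 0.78) | 0.85 / 0.69 (true 0.77) |
| Fixed score + MRI | 0.79 / 0.75 | 0.78 / 0.755 |
| Fixed score with weights off by 60% (SD) + MRI | 0.78 / 0.74 | 0.775 / 0.747 |

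A third run agreed (0.85 / 0.69 refitted; 0.77 / 0.75 with the perturbed score), and the gap widened at 36 men.

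- Optimism of the refitted combined model: 0.86 − 0.69 = 0.17 and 0.85 − 0.69 = 0.16.
- Optimism with the fixed score: 0.79 − 0.75 = 0.04 and 0.78 − 0.755 = 0.025.
- MRI increment in the trial, refitted: 0.86 − 0.77 = 0.09 and 0.85 − 0.76 = 0.09. The true increments are 0.78 − 0.66 = 0.12 and 0.77 − 0.64 = 0.13. The fixed score gave 0.14 in run B.
- Rejection rate for a null MRI term at nominal 5%: 7.9% and 7.5% refitted, 6.1% and 5.4% with the fixed score.

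**Sensitivity to the assumed clinical AUC.** A simpler simulation used 15 or 17 events, 6 or 9 normally distributed clinical predictors and 1,000 trials per setting. At a true clinical AUC of 0.70, the refitted clinical model showed 0.77 to 0.82 in the trial and 0.62 to 0.64 in new data; a fixed score averaged 0.70. Over true AUCs of 0.60 to 0.80 the refitted figures were 0.72 to 0.88 and 0.53 to 0.76. Adding one to three pure-noise MRI terms raised the in-trial AUC by a further 0.01 to 0.05, and the likelihood ratio test rejected in 5% to 22% of trials at nominal 5%.

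**Precision.** By Hanley–McNeil, SE² = [A(1−A) + (n₁−1)(Q₁−A²) + (n₀−1)(Q₂−A²)]/(n₁n₀), with Q₁ = A/(2−A) and Q₂ = 2A²/(1+A). For A = 0.70, SE = 0.085 with 15 events and 0.082 with 17, so the 95% half-width is 0.167 or 0.160. Optimism of 0.16 to 0.17 is as large as the half-width that would be reported.

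**The case against.** A reader might infer that the plan measures MRI's gain over clinical risk against a benchmark fitted to its own data. The documents do not support that: section 12.0 names no clinical-only model and no increment analysis. The firm finding is that the clinical comparator is unspecified. Because no predictors are listed, a calculator risk could itself count as a clinical parameter, and the 6 to 9 coefficients are a count of available fields. That stands, and it is a reason to specify the model.

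A reader might also infer that refitting exaggerates the MRI gain. Under these assumptions it does not. Optimism enters both models and largely cancels, leaving the increment slightly too small.

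Other points stand as limits. The simulations give every man one MRI value, whereas lesion values exist only where there is a lesion. Men can qualify on PSA alone, so eligibility does not fix the DRE result, and section 8.0 lists no DRE field. PBCG is not spelled out in the text available, so linking it to reference 2 is an inference, and its outputs cannot be checked here. The primary outcome is a detection rate, and a background comparison in 31 men does not oblige a pilot to repeat it.

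The strongest argument is that this is ordinary overfitting, which shrinkage or optimism correction would also address. That is partly right. But neither is planned, and correction would lower the reported AUC without improving the model. In new men the fixed-score model does better (about 0.75 against 0.69), and this survives substantial error in the score's weights.

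**Conclusion.** The point holds for the combined models in section 12.0. If clinical variables are entered individually, the reported combined AUC would be about 0.85 to 0.86 where the fitted model achieves about 0.69 in new men and the true value is 0.77 to 0.78. With a fixed score the corresponding figures are about 0.77 to 0.79 and about 0.75. The MRI increment is understated by about 0.03 to 0.04 against its true value (0.05 against the fixed score's own estimate).

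This rests on assumed effect sizes, a coefficient count taken from section 8.0, one MRI value per man, and 15 to 17 events among 50 men. If the analysis covers only men with lesions, the position is worse. It is a secondary analysis in a pilot, so this is a worthwhile improvement and does not threaten the primary outcome.

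**What to change.** In section 12.0:

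- Make the clinical part of the main combined model a single covariate: the logit of the PBCG risk used in the preliminary work (presumably the calculator in reference 2; the team should confirm this and the risk it returns), with only intercept and slope estimated.
- Report PBCG alone, PBCG plus one MRI parameter named in advance, and the AUC difference with a 95% CI. With two slopes there are 15/2 = 7.5 to 17/2 = 8.5 events per coefficient.
- State the unit of analysis: either one index-lesion value per man, or lesions carrying the patient-level score with clustering by patient. Say that men without a lesion value are not in this model.
- Label models with individually fitted clinical variables as exploratory.
- Reconcile the 30% and 17/50 figures.

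In section 8.0, add the DRE result, which section 2.0 counts among the calculator's inputs. Prior biopsy is already settled by the exclusion criteria.

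The cost is SAP wording and one extra field, with no added patients, scans or procedures. The reported combined AUC will be lower. The score may be miscalibrated at a site where section 2.0 says over 60% of diagnosed cases are in African American men; the estimated intercept and slope absorb part of that.

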3.0 Objectives/Aims

This study aims to determine whether a detection specific MRI protocol with quantitative image analysis can improve high grade PCa detection in men with clinical suspicion and no prior biopsy.

Aim 1: Design a PCa detection specific MRI protocol which will facilitate quantitative image analysis and reduce study time by ~50%

Current prostate mpMRI protocols include image sequences and fields of view outside of the prostate gland and its immediate surrounding that are not useful for PCa detection. We will create a detection specific MRI protocol featuring: smaller fields of view zoomed to the prostate, T2 weighted imaging at multiple echo times, chemical exchange saturation transfer imaging (CEST), and DWI at higher b values (up to 4000) that will allow for quantitative prediction of high grade PCa. The exact imaging acquisition parameters can be found in Appendix 3. We expect this MRI protocol to

reduce study (acquisition) time from approximately 45 minutes to 27 minutes, which will potentially lower cost and improve tolerance of the procedure. Significantly, we will omit DCE which will reduce the imaging time, and the risks associated with intravenous contrast including systemic fibrosis, and patient discomfort.

Aim 2: Determine the accuracy of the novel MRI protocol for detection of high grade PCa

50 men with clinical suspicion of PCa (elevated PSA and/or abnormal DRE) will be enrolled into a prospective protocol and will undergo detection protocol MRI described in Aim 1. Quantitative image analyses will be performed to generate SEM maps of DWI. Areas of suspicion for high grade PCa (GS ≥ 7) will be targeted for biopsy. Men with MRI with no areas of suspicion for high grade PCa will undergo standard of care 12 core TRUS biopsy. The primary endpoint will be the rate of detection of high grade PCa on the per patient and per biopsy core basis. Men with biopsy pathology negative for PCa will undergo standard of care (SOC) continued monitoring.

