5.0 Study Design and Procedures

This will be a single arm prospective clinical trial. Men with clinical suspicion for PCa but no prior prostate biopsy will be enrolled from the UI Health Urology clinics. All eligible men will be screened and enrolled by the clinical research coordinator. Enrolled men will undergo detection protocol MRI at the UIC Advanced Imaging Center (AIC) prior to diagnostic biopsy. The image acquisition parameters are listed in the Appendix 3. The MRI will be processed by the study team and evaluated for areas suspicious for high grade PCa by a board certified clinical radiologist ([name]). Subjects with MRI with no suspicious areas for high grade PCa will undergo SOC 12 core TRUS biopsy. Subjects with MRI suspicious for high grade PCa will have 2-4 biopsies guided toward each suspicious lesion using MRI/TRUS fusion biopsies (maximum of 12 cores). All biopsies will undergo SOC histologic processing and interpretation in pathology. Biopsy results will be communicated to the patients by the Urologist performing the biopsy and all additional management will be SOC. This visit will signify the end of the study. See the study schema in Figure 4.

[figure not shown]

Figure 4: Study schema

The primary outcome will be the rate of detection of high grade PCa on a per-patient and per biopsy core basis. The detection rate will be compared between patients with and without evidence of high grade PCa (GS ≥ 7) based on the detection protocol MRI. Secondarily we will analyze the accuracy of the individual MRI parameters including: T2 imaging, ADC, the SEM parameters (DDC and α), the FROC parameters (μ , Δ , β), the Kurtosis model parameters (D, K), and PI-RADS score.

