8.0 Data Collection and Management Procedures

To meet the study goals, clinical, imaging, and pathologic data will be collected prospectively. The co-investigators and other key personnel will have access to the identified data while the subject is on study. A REDCap database will be used to record all of the baseline and clinical data for each subject including: age (continuous in years), self reported race (white, black, Hispanic, other), family history of prostate cancer (positive or negative), serum PSA (continuous, in ng/mL), International Prostate Symptoms Score (IPSS: continuous), Sexual Health Inventory for Men score (SHIM: continuous). All source MRI images from the scanner as well as post-processed images will be collected in Digital Imaging and Communications in Medicine (DICOM) format. Image data will be stored on a password protected server and physically transported from the scanner to the post-processing workstation and to the radiologist workstation using an encrypted flash drive. Data from interpretation of the MRI images to be stored in REDCap will include: PI-RADS score (ordinal), number of lesions (ordinal), and the lesion mean, median, minimum and maximum for each quantitative MRI parameter if applicable. In addition, if applicable each lesion will be outlined on the T2 weighted image series by the radiologist for use at the time of biopsy. At the time of biopsy the prostate volume (continuous, cubic centimeters), type of biopsy (standard or targeted), and number of biopsy cores obtained (ordinal) will be entered in REDCap. Pathology data to be collected and stored in REDCap includes: presence of any carcinoma (Boolean), number of biopsy cores involved with carcinoma (ordinal), location of positive biopsy cores (ordinal lesion number), and maximum GS of biopsies (categorical:

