Appendix 3: Detection protocol MRI imaging acquisition parameters

Hardware:

3 Tesla GE Discovery MR750 (GE Healthcare, Chicago, IL)

Coil: 32-channel pelvic/cardiac phased-array

Acquisition parameters:

Imaging plane: axial

Slice thickness: 3mm

Number of slices: 10-15 (depending on prostate size)

Field of view: 15cm x 15cm using FOCUS

Matrix size: 256x192

DWI

b values: 0, 50, 100, 400, 700, 1000, 1300, 1600, 2000, 3000, 4000 s/mm²

Averages:

b 0-1000: 1

b 1300-2000: 2

b 3000: 4

b 4000: 8

Directions: 3 (x,y,z)

TR/TE = 1538 ms/69.8 ms,

Acquisition time ~3.5 minutes

T2 Mapping

TR: 1900 ms

TE: 14, 28, 41, 55, 69, 83, 97, 110 ms

Acquisition time ~ 5.6 minutes

CEST

Frequency selective saturation pulse at various amplitudes B1 (100 Hz), durations (2 s)

Saturation frequencies: -5 to 5 ppm with 0.25 ppm step size, ±20, and ±100 ppm

Acquisition time ~ 18 min

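### Does the Aim 1 heading's ~50% cut in study time need changing, when the aim's own times give about 40%?

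*Combined protocol and SAP*

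**What the plan says.** Section 3.0 describes Aim 1 twice. The heading is about designing a detection-specific protocol that will "facilitate quantitative image analysis and reduce study time by ~50" per cent. The paragraph under it expects the new protocol to "reduce study (acquisition) time from approximately 45 minutes to 27 minutes", and ties the possible gains in cost and tolerance to that sentence.

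Appendix 3, to which the aim refers for the exact parameters, itemises three sequences:

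- DWI: "Acquisition time ~3.5 minutes"
- T2 mapping: "Acquisition time ~ 5.6 minutes"
- CEST: "Acquisition time ~ 18 min"

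On outcomes, section 5.0 (Study Design and Procedures) states: "The primary outcome will be the rate of detection of high grade PCa on a per-patient and per biopsy core basis". The secondary analyses named there concern the accuracy of individual MRI parameters. Section 8.0 lists the clinical, imaging, biopsy, pathology and complication items to be recorded, and scan duration is not among them. Section 12.0 plans a chi-square test, ROC analyses and regression models, all about high grade cancer. It contains no analysis of time.

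Section 12.0 also has a small mismatch of its own: "we expect a high grade PCa detection rate of approximately 30% or in 17/50 subjects".

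**The concern.** The heading and the text describe the same quantity for the same protocol and do not agree. The text puts acquisition in parentheses after study time, so the heading cannot easily be read as referring to something broader, such as the whole visit. The percentage is also the only number in the heading.

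If that number were a performance target, a 27-minute protocol would meet the text and miss the heading, and the report could be written against either figure. A heading is also easily lifted into an abstract or summary, where the more favourable figure would appear without the minutes that qualify it.

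The pairing of 30% with 17 of 50 in section 12.0 raises a similar question: whether an expected count has been carried wrongly into the design.

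**Working it through.** **Inputs**

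- Stated reduction: ~50% (section 3.0, Aim 1 heading).
- Current and new times: approximately 45 and 27 minutes (section 3.0, Aim 1 text).
- Sequence times: ~3.5, ~5.6 and ~18 minutes (Appendix 3).

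**Step 1: the 27 minutes.** 3.5 + 5.6 + 18 = 27.1 minutes. The text's figure is reproduced.

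**Step 2: the percentage.** Relative reduction = (old − new)/old.

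- With the text's times: (45 − 27)/45 = 18/45 = 40.0%.
- With the Appendix 3 sum: (45 − 27.1)/45 = 17.9/45 = 39.8%.

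The stated ~50% is not reproduced. Dividing by the new time instead gives 18/27 = 66.7%, so a different denominator does not explain it.

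**Step 3: what 50% would need.** From 45 minutes, the new protocol would have to take 0.5 × 45 = 22.5 minutes, which is 27.1 − 22.5 = 4.6 minutes less than the listed sequences. With the sequences as listed, the current protocol would have to take 27.1/0.5 = 54.2 minutes. Nothing in the documents points to that baseline.

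**Step 4: could rounding explain it?** The documents do not define approximately 45. As an assumption, take it as rounded to the nearest 5 minutes (42.5 to 47.5), and take each sequence time as rounded to its last digit:

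- shortest total: 3.45 + 5.55 + 17.5 = 26.5 minutes
- longest total: 3.55 + 5.65 + 18.5 = 27.7 minutes

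| Baseline (min) | New time (min) | Reduction |
|---|---|---|
| 42.5 | 27.7 | 14.8/42.5 = 34.8% |
| 45 | 27.1 | 17.9/45 = 39.8% |
| 47.5 | 26.5 | 21.0/47.5 = 44.2% |
| 50 (looser assumption) | 26.5 | 23.5/50 = 47.0% |

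Only the loosest reading, with every input at its most favourable value, comes near 50%. At the stated values the answer is 40%.

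**Step 5: where the percentage is used.**

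| Part of the plan | Does it use scan time? |
|---|---|
| Outcomes (section 5.0, Study Design and Procedures) | No: detection of high grade cancer and accuracy of MRI parameters |
| Recorded data (section 8.0) | No duration item listed |
| Analyses (section 12.0) | No |
| Success criterion for Aim 1 | None stated |
| Cost and tolerance rationale (section 3.0) | Tied to the 45-to-27-minute sentence, not to the percentage |

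**Step 6: the count in section 12.0.** 0.30 × 50 = 15, and 17/50 = 34%. The two differ by 2 men, or 4 percentage points. The same section says that no power analysis is needed for this single-arm pilot, so neither figure sets the sample size, and neither appears in the planned chi-square test.

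**The case for a change.** The strongest case for a change is that the error is certain, can be checked from the document alone and costs one phrase to correct. The heading overstates the saving by a quarter of its true value (50/40 = 1.25), in the favourable direction. Appendix 3 independently confirms the 27 minutes, so it is clear which figure is out of line. The approximation signs do not rescue it either: a gap of 10 points is more than ordinary rounding of the inputs produces.

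All of that stands as arithmetic. What does not stand is the step from a mismatch to a consequence. Aim 1 is to design a protocol, and its parameters are already fixed in Appendix 3. The plan sets no threshold of time saved and provides for no measurement of it, so there is no test that the study could pass on one figure and fail on the other. The risk that the heading is quoted alone is a matter of care in reporting, and the minutes needed to report correctly are given under the same heading.

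Raising the baseline to about 54 minutes so that the percentage comes out right would be worse than the slip, since it would fit an input to a desired result.

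**Conclusion.** The heading is wrong by its own text: about 40% (39.8% with the Appendix 3 sum), not ~50%, or 18 minutes saved instead of 22.5. Under the assumed rounding of the inputs the reduction lies between about 35% and 44%, or up to 47% if the baseline is stretched to 50 minutes. The central result needs none of these assumptions.

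No change to the plan follows. This is a clerical slip in a descriptive heading. Whichever percentage is printed, the scans, biopsies, outcomes, recorded data and analyses are the same. Authors who report the saving can state the minutes, or about 40%, from what the plan already contains. The 30% against 17 of 50 (34%) in section 12.0 is a separate slip of the same kind and also feeds no calculation. Both could be tidied if the document is reopened for another reason, but neither is a reason to reopen it.

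The conclusion rests on scan time staying outside the outcomes and analyses, as it does now.
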